Infants fed diets supplemented with DHA have higher levels of DHA in red blood cell phospholipids [13], and have demonstrated improved functional outcomes [14, 15]. While dietary sources of DHA may ultimately qualify as semi-essential for the preterm infant, DHA is currently lacking in the intravenous nutrition used in neonatal intensive care units (NICU) [16]. Current estimates are that 67 mg/day of DHA is accumulated *in utero* during the last trimester [2] The American Academy of Pediatrics recommends that preterm infant feeding goals mimic intrauterine nutrient intake as the most logical approach to achieving appropriate nutritional levels [17]. However, stable isotope studies indicate a preterm intake of only 4 mg/day [18], far below intrauterine nutrient intake. Human milk is the preferred enteral nutrition for the preterm infant and contains vital anti-infective properties but milk DHA concentrations vary among mothers, dependent on maternal dietary intake [19-22]. Previous studies have demonstrated that fatty acid supplementation improves human milk fatty acid composition [23, 24] but *levels of human milk DHA that would approximate in utero accretion for the human milk-fed preterm infant have never been targeted*.

Epidemiologic studies have demonstrated that maternal intakes of 1 gram of DHA correspond to 1 mole weight % in human milk [25]. Dietary intake of DHA up to 3 grams per day are considered GRAS by the FDA [26]. A diet of human milk with 1% DHA at 150 ml/kg would better achieve intrauterine intake of 67 mg/day. Animal studies have shown reduced rates of necrotizing enterocolitis (NEC) when fed omega-3 fatty acid supplemented diets [27]. A dietary strategy that seeks to approximate intrauterine accretion values of DHA by improving the mother's diet could therefore promote improved nutrient availability and more appropriate immune response in preterm infants. In our previous 2 years we have demonstrated that the current milk composition of DHA is less than optimal for the preterm infant [28] and that a RCT of 1 gram maternal dietary DHA intake vs. a placebo soy oil resulted in enhanced DHA milk composition equal to intrauterine concentration provided to the NICU infant ([name], 2011 manuscript in review)- figure 2.

Figure 2: Milk concentration of DHA in DHA supplemented women, [name], Breastfeeding Medicine, 2012

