Study Design: We propose a prospective, randomized, trial of oral DHA supplementation of lactating mothers. Cincinnati Children's Hospital research staff will screen all infants admitted to the Cincinnati University Hospital NICU on a weekly basis. Eligible participants will be identified by the Principle Investigator and the research coordinator. Potential participants (mothers) will be approached regarding the possibility of study participation by study staff trained in the consent process. Eligible participants will be screened and if eligible and interested, will be consented within one week of being admitted to Cincinnati University Hospital NICU. Maternal consent will be obtained for the infant. Consent will be administered by Cincinnati Children's Hospital Medical Center staff trained in the consent process and having completed all required CITI training. Informed consent will be documented by an Informed Consent Process Note. All data and infants biological sample collection will take place during the infants stay in Cincinnati University Hospital NICU. Mother's biological samples will be collected by Cincinnati University Hospital NICU. Study staff and Hoxworth outpatient lab.

After informed consent, lactating mothers will be randomized by The Cincinnati University Hospital Investigational Pharmacy to receive DHA (DHA- Martek Biosciences, now known as DSM Nutritional Lipid- Expecta®) 200 mg, or 1000 mg/day. The randomization schedule has been devised in collaboration with the Biostatistics expert, [name], identified in these studies. We have used the Consolidated Standards of Reporting Trials (CONSORT)framework [33].

Participants who meet any exclusion criteria during the course of the study, are non-compliant or are lost to follow-up will be withdrawn. Provided that there are at least 8 mother/baby pairs with evaluable data in each group, withdrawn participants will not be replaced. Anticipated enrollment will take two years.

Inclusion criteria: Lactating mothers at Cincinnati University Hospital with infants born at <29 weeks gestation admitted to The Cincinnati University Hospital NICU

Exclusion criteria:

- Infants with the presence of congenital anomalies (trisomy 13, 18, 21, urethral, gastrointestinal and cardiac defects) that affect the standard course of care.
- mother's <18 and
- mothers with known allergy to algeal source

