Statistical Plan: All data analyses will employ intention to treat principles. In our primary analysis, ANOVA will be used to compare DHA levels at four weeks in the breast milk of mothers assigned to the different concentrations of DHA supplements. As in any prospective study, If we experience substantial loss to follow-up (e.g., > 10% of subjects), we will fit a linear mixed model [35] We will use two sample t tests to compare infant blood DHA concentrations and TNF-alpha and IL-10 levels at 8 weeks of infants randomized to DHA-supplemented milk. The comparison of DHA concentrations will be performed at a significance level of 0.05 while the comparison of TNF-alpha and IL-10 levels will be performed at a significance level of 0.025 to adjust for the two outcomes. All analyses will be performed using SAS (SAS Inc., Cary, NC). Our sample size determination to detect a two-fold difference in the DHA levels at four weeks in expressed milk of mothers assigned DHA treatments, we will need data on a total of 16 mothers at week 4 (8 per group). This sample size calculation was based on 90% power, a two-sided significance level of 0.025, and a coefficient of variation (CV) of 30%; the CV is based on a previous study [36]. Assuming a conservative 20% loss to follow-up before week 4, we will enroll enough mother-infant pairs to achieve our desired sample size of 16 at 4 weeks. It is expected that evaluable data at week 4 from at least sixteen of the mother/baby pairs (8 pairs per group) will be obtained. The University Hospital Investigational Pharmacy will randomize participants per the Consolidated Standards of Reporting Trials (CONSORT) framework. Secondary outcomes will use linear mixed models and Bonferroni correction.

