Among participants with adequate quality milk fat layer RNA at Week 4, five pairs will be randomly selected from each group for sequencing (matched on gestational week of delivery, milk DHA concentration at baseline, and Week 4 breast milk output level (exceeds, at, or below infant's needs). The remaining will be set aside for future studies. RNA integrity (RIN \geq 7) will be confirmed at the microarray core and then sent to the gene discovery core for RNA-Seq library preparation (Illumina TruSeq RNA kit) and sequencing (Illumina Hi-Seq2500). Libraries will be multiplexed in batches of 10 with at least 30 million 150bp paired-end reads per sample. Sequence reads will be trimmed for quality and then aligned to the human genome using TopHat. We will use Cufflinks to determine gene expression levels, normalized to Fragments Per Kilobase of transcript per Million mapped reads (fpkm). We will identify differentially expressed genes using DESeq and intersect this gene list with known cytokine signaling genes. We will also conduct Gene Set Enrichment Analysis. Significant biomarker genes will be assayed for all participants using TaqManTM qPCR. Power: N=5 pairs per group enables 90% power (α =0.05) to detect 1.5-fold differences between DHA versus placebo for moderate to high abundance genes (FPKM \geq 10) and 3.0-fold differences for low abundance genes (FPKM \sim 1.0).

[name] PhD.,

The University of Cincinnati / Cincinnati Children's Hospital Medical Center, Docosahexaenoic Acid Supplementation to Mothers to Improve Preterm Infant Nutrition and Immune Homeostasis

July 12, 2013

Safety: All records will be kept according to IRB and regulatory standards. All PHI will be stored in a password protected database. All biological sample data will be kept in a separate database from PHI and study identifiers. Written research records, participant contact information, and signed consent forms will be kept in a locked file cabinet near the study coordinator's work station. All data will be entered from source documents into a Redcap database using a password protected, secure server. Individually identifiable information will not be included in the data set or in any reports.

Laboratory samples will be de-identified and stored at Cincinnati Children's Hospital Medical Center and Nationwide Children's in Columbus Ohio.

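### The primary milk DHA analysis should be one named model, adjusted for baseline on the log scale, instead of an unadjusted week-4 ANOVA with a mixed model added at a loosely worded loss trigger (minor, low-cost improvement)

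*Combined protocol and SAP*

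**What the plan says.** The Statistical Plan sets the primary analysis as follows: "In our primary analysis, ANOVA will be used to compare DHA levels at four weeks in the breast milk of mothers" in the two dose groups. No covariate is named. The next sentence reads: "If we experience substantial loss to follow-up (e.g., > 10% of subjects), we will fit a linear mixed model". It does not say whether that model replaces or supplements the ANOVA. It gives no terms, covariance structure or contrast, and does not say at which visit loss is counted. The 10% is given only as an example.

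Related statements:
- The same section sizes the trial with a loss allowance: "Assuming a conservative 20% loss to follow-up before week 4".
- It commits to assignment-based analysis: "All data analyses will employ intention to treat principles".
- It uses mixed models elsewhere with no loss condition: "Secondary outcomes will use linear mixed models and Bonferroni correction".
- Study Procedures schedules milk at the start of supplementation and at weeks 2, 4 and 8, so a baseline value is planned for every mother.
- The Background says "milk DHA concentrations vary among mothers, dependent on maternal dietary intake", and the RNA-sequencing paragraph selects samples "matched on gestational week of delivery, milk DHA concentration at baseline".

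**The concern.** Two gaps sit together. First, once loss passes a loosely worded threshold there may be two primary results, and the plan does not rank them. Only the primary outcome has a conditional method; the secondary outcomes do not. Second, the plan treats baseline milk DHA as relevant when it picks RNA samples, yet leaves it out of the main comparison. With 8 mothers per group, a chance difference in baseline DHA could be noticeable.

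What is at stake is a primary result fixed in advance and, if baseline predicts week 4 well enough, a narrower interval for the dose contrast. The validity of the trial is not at stake.

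**Working it through.** **Inputs from the Statistical Plan:** two-fold difference, CV 30%, two-sided 0.025, 90% power, 8 per group at week 4, 20% loss allowance, trigger at more than 10%. The scale (raw or log) is not stated. I use 0.025 because the sample size does; the section also gives 0.05 for DHA concentrations without making clear whether that covers milk.

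**1. Reproduce the stated sample size.** Raw scale, means 1 and 2, SDs 0.3 and 0.6: root-mean-square SD = sqrt((0.09 + 0.36)/2) = 0.474. The noncentral t calculation needs 8 per group (power 94.3%). Simulation with the unequal SDs gives 91.8% (Welch) and 93.9% (pooled) at 8 per group, against 85.8% and 89.3% at 7. The stated 16 reproduces.

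**2. The same design on the log scale.** SD = sqrt(ln(1 + 0.3²)) = 0.294; effect ln 2 = 0.693. With 8 per group and 14 df, power is 97.9%. The fold difference detectable with 90% power is 1.77.

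**3. Effect of baseline adjustment.** With correlation ρ between baseline and week 4, adjustment multiplies the variance by 1 − ρ². Estimating the slope from 16 mothers costs a factor 1 + 1/(16 − 4) = 13/12 = 1.083 and one degree of freedom (13 left). The ratio to ANOVA is (1 − ρ²) × 13/12. All values of ρ are assumptions.

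| ρ | Variance ratio | Power at two-fold | Detectable fold, 90% power | 97.5% interval for dose ratio, ×/÷ |
|---|---|---|---|---|
| ANOVA | 1 | 97.9% | 1.77 | 1.445 |
| 0.1 | 1.07 | 96.8% | 1.81 | 1.470 |
| 0.3 | 0.99 | 97.9% | 1.77 | 1.446 |
| 0.5 | 0.81 | 99.3% | 1.68 | 1.398 |
| 0.7 | 0.55 | >99.9% | 1.53 | 1.318 |

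Break-even is ρ = sqrt(1/13) = 0.28, or 0.31 once the lost degree of freedom is counted.

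**4. What a mixed model adds.** With the covariance known and 2 mothers per group lost after week 2, using their earlier milk lowers the variance ratio by a further 0.01 to 0.02 (compound symmetry) or 0.02 to 0.05 (decaying correlation), for ρ from 0.3 to 0.7. Mothers lost before week 2 add nothing. Nearly all the gain comes from the baseline value.

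**5. Why the scale matters.** Assume mean milk DHA rises from 0.1 at baseline (the figure in the Abstract, read as the measured level) to 0.8 (the Abstract's target), with CV 30% throughout. The raw SDs are then 0.3 × 0.1 = 0.03 and 0.3 × 0.8 = 0.24, an eight-fold difference that a common-variance structure ignores. In simulations with no dose effect and nominal 2.5%, a compound-symmetry mixed model on raw values gave type I error of about 4% to 6% with 14 df. Baseline-adjusted ANCOVA on log values gave 2.3% to 2.7%.

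**6. How often the trigger would fire.** If 16/(1 − 0.20) = 20 mothers were enrolled, more than 10% means 3 or more lost. The binomial probability is 79% at 20% true loss, 60% at 15%, 32% at 10% and 7.5% at 5%.

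**The case against.** The strongest reply is that nothing here is wrong. An unadjusted comparison is valid after randomisation, the sample size reproduces and power is ample. The mixed-model sentence directly follows the primary-analysis sentence and can be read as replacing it, and one added line would settle that. Adjustment for baseline is then a preference resting on an unknown correlation, which may be low: baseline milk comes from the first week of life, before supplementation, and the Abstract reports dietary intake of 23 mg/day against assigned doses of 200 or 1000 mg/day. Matching on baseline DHA for RNA selection says nothing about that correlation. All of this stands. It sets the weight at minor, but does not remove the case for using a value already collected and naming one primary result.

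Four stronger readings are tempting, and the documents do not support them.
- *The plan expects the trigger to fire.* The 20% is called conservative, so it is a margin and not a forecast. Enrolment of 20 is derived, not stated, and Study Design implies that withdrawn pairs may be replaced if a group falls below 8 evaluable pairs. The 79% is an upper planning case.
- *The conditional model inflates type I error.* The trigger depends on how many mothers are lost, not on their results. A free choice between the two tests would raise 0.025 to about 0.034 to 0.042 for ρ from 0.3 to 0.7, but the plan does not allow a free choice.
- *The ANOVA breaks intention to treat.* Study Design says "Participants who meet any exclusion criteria during the course of the study, are non-compliant or are lost to follow-up will be withdrawn", but not that milk already given is discarded. Retaining such mothers' earlier milk changes the variance ratio by 0.05 at most.
- *A mixed model should simply become primary.* On raw values with a simple covariance structure, that could replace a valid test with an anti-conservative one.

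**Conclusion.** The point holds as a minor, cheap improvement. The plan leaves the primary result unranked when loss is substantial and does not use the baseline milk DHA it collects. At the planned two-fold difference the conclusion would rarely change. The benefit is a primary result fixed in advance, whatever the correlation, and a narrower interval only if that correlation exceeds about 0.3. At an assumed 0.1 the cost is about 7% more variance, with power still about 97%; at 0.7 the variance falls by about 45%. These figures assume log-normal milk DHA with CV 30%, 8 mothers per group and two-sided 0.025.

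**What to change.** Replace the ANOVA and trigger sentences with one short paragraph:
- **Primary, whatever the loss:** the week-4 contrast between assigned groups on log-transformed milk DHA, by ANCOVA with log baseline milk DHA as covariate (13 df at 8 per group). Include every mother with a week-4 sample, as assigned, and state in advance how a missing baseline value is handled.
- **Sensitivity:** the unadjusted week-4 ANOVA, and a log-scale linear mixed model on all scheduled milk samples, which uses milk from mothers lost before week 4. Pre-specify its covariance structure and a small-sample degrees-of-freedom method.
- **Delete** the 10% trigger and **state the log scale** explicitly.

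No extra samples, visits or mothers are needed, the 16 evaluable mothers stay as planned, and mixed models are already in the plan for secondary outcomes. The downside is the small loss of precision if baseline and week-4 milk DHA turn out to be weakly correlated.

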Study Design: Breast milk providers for enterally-fed preterm infants <29 weeks gestational age will be randomized to receive daily oral supplementation with DHA at 200mg or 1000mg. Based on our previous study with a placebo, it was apparent that even motivated mothers had a paucity of DHA in the diet and in their prenatal supplement therefore we felt it important to randomize to at least the baseline 200mg per day and then added the other dose as the target optimal dose for milk concentrations to achieve 0.8 mol weight percent. This concentration of DHA would provide intrauterine accretion when fed at 150ml/kg per day in the NICU. DHA concentration will be analyzed by gas chromatography in milk and infant cell membranes. Milk and infant plasma cytokine levels and cytokine production capacity will be measured. All samples will be obtained at baseline (within first week of life), weeks 2, 4, and 8. Inflammatory complications (BPD, NEC, and ROP) will be tracked. Cytokine gene expression from RNA extracted from the Week 4 milk samples will also be examined. Stool samples will not only have fatty acids but also bacteria and yeast analyzed.

Significance: Our unique investigation of maternal supplementation to improve DHA delivery to preterm infants represents the first study of its kind.

Purpose

The objective of this project is to improve preterm infant intake of DHA that approximate the levels obtained by fetal accretion during the third trimester of pregnancy and determine if there are functional relationships to inflammation, growth, and development.

The following specific aims will test the hypotheses that:

Aim 1: Maternal DHA supplementation will improve plasma and milk DHA concentration in the mother and preterm infant

Aim 2: Higher intakes of dietary DHA will decrease expression of pro-inflammatory cytokines and increase expression of anti-inflammatory cytokines in the plasma and milk samples of

breast feeding mother - infant dyads through the alteration of sRAGE signaling. This will result in an improved microbiome as evidence of bacteria and yeast in stool samples.

Background:

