- mothers with history of bleeding disorders or taking any other medication that may increase the risk of bleeding
- infants with bleeding disorders or receiving any other medication that may increase the risk of bleeding

Study Procedures:

Maternal Dietary intake and breastmilk samples will be collected and assessed at initiation of supplementation and at weeks 2, 4, and 8. Maternal breast expression and breastfeeding patterns; anthropometry (weight, height, circumferences); exercise patterns; and smoking habits will be obtained at week 4.

Maternal blood and buccal swabs (saliva) will be collected and assessed at baseline and at weeks 4, and 8.

Infant Dietary intake, blood samplesbuccal swabs (saliva), and stool samples will be collected and assessed at baseline and at weeks 2, 4, and 8. – see Figure 3.

Maternal blood collected will be 5 mL at each collection therefore a total of 15 mL whole blood collected for the study. Infant blood collected will be \sim 1 mL at each collection therefore a total of \sim 5 mL whole blood collected. The infant blood will be collected during routine nutritional lab collections which are clustered with standard of care.

The dietary and supplemental intake of the mother will be assessed at The Bionutrition Center using NDSR software and the dietary intake of the infant will be calculated by the Neonatal Dietitian. The fatty acid contents of the breastmilk, blood, and stool samples will be measured by gas chromatography in our laboratory_using Bligh-Dyer extraction (Chloroform: Methanol (2:1))[34]. Cytokine (IL-10, IL 6, IL-8, IL 1B, TNF a, TGF, adiponectin, leptin) and sRAGE concentrations will be examined in maternal milk, and maternal and infant blood samples using a MSD SECTOR® Imager 2400A. This instrument allows for the analyses of 40 individual samples in duplicate at one time using a 96-well format. Infant growth, clinical outcome, and development data will be collected. Breastmilk samples will be analyzed for fatty acids and certain proteins as is routinely analyzed at Human milk banks of North America and clinically at Cincinnati Children's Hospital Medical Center. Cytokine analysis will be performed on infant stool samples. Saliva samples will be analyzed for genetic polymorphisms. Buccal swabs (saliva) will be analyzed for fatty acids.

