An additional teaspoon of fresh milk will be collected at Week 4 and aliquoted into whole, aqueous, and fat layer fractions. Fat layer RNA will be isolated using a MaxwellTM 16 integrated system (Promega, Madison, WI). RNA quantity (target=1000 ng) and quality (A260:A280 target \geq 1.9) will be confirmed prior to RNA sequencing. Na:K ratio, as a marker of mammary gland inflammation, will be assayed on the milk aqueous fraction.

All biological samples will be collected within study time frames as feasible.

Stool will also have bacteria and yeast measured by using 16S ribosomal markers. **Growth and Hospitalization**

Growth measures are standard of care at University NICU and include weekly weight, length, and head circumference measurements and will be extracted from the participant's charts. At discharge we will obtain body composition on the infant using a validated isolette that has non-invasive, volume and mass measurement capability. Cincinnati University Hospital course records that could be pertinent to the study outcomes will be collected from both mother and infant. Compliance will be assessed as part of diet record evaluations; rate of compliance will not be assessed

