Maternal blood – fatty acids Diet analysis Buccal swabs (saliva) Infant blood - fatty acids, cytokines, and sRAGE Nutrition labs Growth measures: Weight, length, head circumference Diet analysis Stool from diaper Buccal swabs (saliva)	Infant blood - fatty acids and cytokines labs, sRAGE Stool from diaper Buccal swabs (saliva) Growth measures	Maternal blood – fatty acids Diet analysis Exercise and Smoking habits Breast milk expression and breastfeeding patterns and concerns Anthropometry (weight, height and circumferences) Buccal swabs (saliva) Infant blood fatty acids and cytokines labs, sRAGE Stool from diaper Buccal swabs (saliva) Growth measures	Buccal swabs (saliva) Infant blood - fatty acids and cytokines labs, sRAGE Buccal swabs (saliva) Stool from diaper Growth measures Body composition using the Pea Pod ® air displacement isolette

Figure 3. Study	time table for r	recruitment, samp	ole, and data collection

Summary and Significance:

Premature birth is responsible for 75% of perinatal death [37]. Inflammatory conditions such as necrotizing enterocolitis (NEC), bronchopulmonary dysplasia (BPD), and retinopathy of prematurity (ROP) in the preterm infant are a tremendous source of morbidity and mortality. DHA is a key regulator of inflammation. Breast milk is the ideal delivery vehicle for DHA based upon the ability of the breast to provide balanced fatty acid composition as well as anti-infective molecules. Further understanding of the mechanisms could ensure our nutritional strategy is optimal.

References:

- 1. Fanaroff, A.A., et al., *Trends in neonatal morbidity and mortality for very low birthweight infants*. Am J Obstet Gynecol, 2007. **196**(2): p. 147 e1-8.
- Innis, S.M., Essential Fatty Acid Transfer & Fetal Development. Placenta, 2005. Suppl A: p. S70-75.
- 3. Turner, N., P.L. Else, and A.J. Hulbert, *Docosahexaenoic acid (DHA) content of membranes determines molecular activity of the sodium pump: implications for disease states and metabolism.* Naturwissenschaften, 2003. **90**(11): p. 521-3.
- 4. SanGiovanni, J.P., et al., *Meta-analysis of dietary essential fatty acids and long-chain polyunsaturated fatty acids as they relate to visual resolution acuity in healthy preterm infants.* Pediatrics, 2000. **105**(6): p. 1292-8.
- 5. Innis, S.M., *Perinatal biochemistry and physiology of long-chain polyunsaturated fatty acids*. J Pediatr, 2003. **143**(4 Suppl): p. S1-8.

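### The three infant week-8 comparisons are unadjusted t tests although the same assays are scheduled at baseline; adjusting for baseline gains power if the correlation exceeds about 0.3

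*Combined protocol and SAP*

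**What the plan says.** The Statistical Plan sets out the infant comparisons in one sentence: "We will use two sample t tests to compare infant blood DHA concentrations and TNF-alpha and IL-10 levels at 8 weeks". It names no covariate and no change score. On the error rate it says "The comparison of DHA concentrations will be performed at a significance level of 0.05", and it gives TNF-alpha and IL-10 0.025 each.

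Baseline values of the same outcomes are planned in three places:

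- The abstract, under Study Design: "All samples will be obtained at baseline (within first week of life), weeks 2, 4, and 8".
- Study Procedures, in the sentence listing infant diet, blood, saliva and stool: "stool samples will be collected and assessed at baseline and at weeks 2, 4, and 8". The cytokine panel in that section includes TNF-alpha and IL-10 and covers infant blood.
- Figure 3, baseline column: "Infant blood - fatty acids, cytokines, and sRAGE".

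Other passages show that a baseline may be absent or late. Study Procedures says "The infant blood will be collected during routine nutritional lab collections which are clustered with standard of care" and "All biological samples will be collected within study time frames as feasible". Under Study Design, mothers "will be consented within one week of being admitted to Cincinnati University Hospital NICU".

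The Statistical Plan mentions mixed models twice. The first, for loss to follow-up above about 10%, comes directly after the milk DHA analysis. The second is its closing sentence, which assigns mixed models with a Bonferroni correction to secondary outcomes without naming them. Neither mentions a baseline covariate.

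**The concern.** Infant DHA belongs to Aim 1 and the infant cytokines to Aim 2, but the only sample size for a trial endpoint is for week-4 milk DHA. With 8 infants per arm, the t tests have 80% power only for very large differences: 1.70 SD for a cytokine and 1.51 SD for infant DHA. An infant's own earlier value of the same assay is often the most useful covariate available. Here it is already scheduled, so using it needs no further blood.

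There is also an ambiguity. If these three outcomes count as secondary, the plan gives them two methods, a t test and a mixed model. On either reading no baseline adjustment is specified, so the choice would be left until the data are in hand.

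**Working it through.** **Inputs from the plan.** 8 per group evaluable (stated for week 4 only); alpha 0.05 for infant DHA and 0.025 for each cytokine.

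**Assumptions.** The same 8 per arm at week 8; one infant per mother; two-sided tests (sidedness is stated only for the sample size); normal outcomes on the analysis scale; baselines missing at random. The baseline to week-8 correlation ρ is not given, so 0, 0.3, 0.5 and 0.7 are shown.

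**1. The plan's own figure.** Take a two-fold difference in milk DHA as means 1 and 2. A CV of 30% gives SDs 0.3 and 0.6 and an average variance of (0.09 + 0.36)/2 = 0.225. At two-sided 0.025, a t test has 89.9% power with 7 per group and 94.3% with 8. For 90% power that means 8 per group, as stated.

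**2. The planned t test.** Degrees of freedom are 2 × 8 − 2 = 14. For a difference of d SD the noncentrality is d√(n/2), which for d = 1.5 is 1.5 × √4 = 3.0.

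- Alpha 0.025 (critical value 2.510): power 68.7%.
- Alpha 0.05 (critical value 2.145): power 79.7%.
- Detectable at 80% power: 1.697 SD and 1.507 SD.

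**3. Break-even correlation.** Adjusting for one random baseline multiplies the variance of the treatment difference by (1 − ρ²) × (N − 3)/(N − 4), which is (1 − ρ²) × 13/12 at N = 16.

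- Variance alone: 1 − ρ² = 12/13, so ρ = √(1/13) = 0.277.
- Counting the lost degree of freedom, at alpha 0.05: 1 − ρ² = (12/13) × (2.145/2.160)² = 0.910, so ρ = 0.300.
- The same at alpha 0.025, with 2.510 and 2.533: ρ = 0.306.

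Solved from exact power, break-even is 0.28 to 0.31 when the t test has 50% to 90% power. It depends on the number with week-8 data: 0.34 to 0.38 at 6 per arm, 0.31 to 0.34 at 7, 0.25 to 0.26 at 10.

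**4. Power for a 1.5 SD difference.** ANCOVA figures are from 200,000 simulated trials per cell.

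| Alpha 0.025 (each cytokine) | ρ = 0 | 0.3 | 0.5 | 0.7 |
|---|---|---|---|---|
| t test | 69% | 69% | 69% | 69% |
| ANCOVA, all baselines | 64% | 69% | 78% | 92% |
| One missing per arm, pooled-mean imputation | 64% | 68% | 76% | 88% |
| One missing per arm, complete cases | 56% | 60% | 69% | 86% |
| Two missing per arm, pooled-mean imputation | 64% | 68% | 74% | 84% |
| Two missing per arm, complete cases | 46% | 49% | 58% | 76% |

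| Alpha 0.05 (infant DHA) | ρ = 0 | 0.3 | 0.5 | 0.7 |
|---|---|---|---|---|
| t test | 80% | 80% | 80% | 80% |
| ANCOVA, all baselines | 76% | 80% | 87% | 96% |
| One missing per arm, pooled-mean imputation | 76% | 79% | 85% | 94% |

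At alpha 0.025 and 1.5 SD, break-even with imputation is 0.30, 0.31 and 0.35 for zero, one and two baselines missing per arm. With complete cases it rises to 0.49 and 0.63 for one and two missing. Most of the benefit therefore depends on keeping infants whose baseline is missing.

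**5. Type I error.** Under no treatment effect, rejection was 0.023 to 0.026 at nominal 0.025 and 0.049 to 0.051 at nominal 0.05, imputation included.

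**The case against.** The t tests are valid, so this is a choice between two legitimate analyses, and even the direction of the benefit rests on a correlation the documents do not give. There is reason to expect a modest one: baseline is in the first week of life in infants born before 29 weeks, the last sample is about eight weeks later or at discharge, and the intervention is meant to change DHA in between. Cytokines may not be normal. Nor does adjustment remove the underlying limit: at a correlation of 0.5 the detectable cytokine difference is still 1.54 SD. Finally, a mixed model under the closing sentence could use baseline as a repeated response.

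Much of this stands. The gain is conditional, and it shrinks as baselines are lost. With four of eight unusable per arm, imputed power is 64, 66, 70 and 76% at the four correlations against 69% for the t test, and break-even is about 0.45. With 6 infants per arm and two unusable, it is about 46, 48, 52 and 61% against 51%.

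Two things keep the point alive. First, the trade is uneven. With 8 per arm and all baselines, a cytokine test loses about 4 points at zero correlation but gains about 9 at 0.5 and 23 at 0.7. Second, the mixed-model reading does not settle the matter: the plan names t tests for these outcomes, does not say they are among the secondary ones, and does not say how a mixed model would treat baseline.

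**Conclusion.** The point holds as an improvement in efficiency; there is no error or bias to correct. The planned infant tests leave out baseline values of the same assays that the trial already schedules, and nothing else in the plan clearly brings them in. With 8 infants per arm at week 8 and few baselines missing, adjustment raises power once the baseline to week-8 correlation passes about 0.3. It makes no difference near 0.3 and costs about 4 points near zero. At a correlation of 0.5 the difference detectable with 80% power falls from 1.70 to 1.54 SD for a cytokine and from 1.51 to 1.36 SD for infant DHA. At 0.7 it falls to 1.27 and 1.13 SD. Confidence is medium because the correlation, the number of infants at week 8 and the number of usable baselines are all unknown. The change is worth making but is not essential to the trial's validity.

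**What to change.** Before any outcome data are seen, amend the Statistical Plan as follows.

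1. Replace the three t tests with a week-8 ANCOVA for each outcome, with treatment and the infant's own baseline value as terms. Put outcome and baseline on the same pre-specified scale, for example log for the cytokines.
2. Keep the stated levels: 0.05 for infant DHA, and 0.025 each for TNF-alpha and IL-10.
3. Include every randomised infant with a week-8 value. If the baseline is missing, or was drawn after the mother's first study dose, replace it with the mean of all usable baselines in both arms combined, ignoring arm.
4. State that the closing sentence on secondary outcomes covers only the remaining outcomes.

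This costs SAP wording and a little programming, and no new samples. One degree of freedom is spent: at zero correlation, power for a 1.5 SD difference falls from 68.7% to 64.4% for a cytokine and from 79.7% to 76.1% for infant DHA. Item 3 should not be dropped. Without it, one missing baseline per arm takes the cytokine figure from 69% to 56% at zero correlation.
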